**Endpoints:**

**Primary endpoint:** The ongoing pregnancy rate in the first frozen embryo transfer cycle.

**Secondary endpoint:** LH, Estradiol, and Progesterone profile (Day 1, day 5, and day 8 of ovarian stimulation, final oocyte maturation day, and 12 hours after the final oocyte maturation injection), premature LH rate, the duration of ovarian stimulation and the total dose of FSH, the number of ovarian stimulation cycles, number of cumulus-oocyte complexes, number of MII oocytes, oocyte survival rate, fertilization rate, embryo-cleavage rate, blastocyst rate, top-quality blastocyst rate, blastocyst survival rate, implantation rate, positive pregnancy rate, clinical pregnancy rate, early miscarriage rate, multiple pregnancy rate, ectopic pregnancy rate, drop-out rate, OHSS rate, and adverse events.

**Study Population:**

Couples who undergo IVF treatment at ART Unit – Tam Anh General TP. Ho Chi Minh (IVFTA HCM) and ART Unit – Tam Anh General hospital (IVFTA HN) fulfill the inclusion and exclusion criteria

**Inclusion criteria:**

- Women's age between 18 and 37 years
- AFC  $\leq 5$  and/or AMH  $\leq 1.2$  ng/ml
- Agree to perform single frozen blastocyst embryo transfer

**Exclusion criteria:**

- Oocyte recipient
- Indication of preimplantation genetic testing
- Known allergic reactions to medications in the Study (progesterone products, GnRH antagonist....)
- Basal FSH above 15mIU/mL.
- Have contraindications of ART treatment (e.g. critical or acute diseases)
- Retrieved sperm
- Repeated Implantation failure (had more than three failed embryo transfers with good quality embryos)
- Inability to comply with the study procedures

- Patients with a history of thyroid cancer who are on hormone replacement therapy or those diagnosed with thyroid diseases at the time of eligibility assessment

**Description of Sites/Facilities Enrolling Participants:**

Site enrolling:

- IVFTA HCM (Tam Anh TP. Ho Chi Minh General hospital)
- IVFTA HN (Tam Anh General hospital)

IVFTA HCM has a volume of about 1700 - 2000 cycles per year. Of these, 67% of patients were under 37 years old, and 45% had a low ovarian reserve. Frozen embryo transfer is 97% of all cycles. The embryo and gamete cryopreservation system at IVFTA-HCM is well established for cryopreservation requirements in oocyte accumulation strategy. Quality management was applied with RTAC's code of practice.

**Description of Study Intervention:**

After written consent is obtained, the patient will undergo ovarian stimulation from the second-fourth day of menstruation after randomization to either arm:

1. Intervention arm: Women will receive oral Dydrogesterone 10mg (Duphaston 10mg) t.i.d daily from the first day of ovarian stimulation till the day of final oocyte maturation.
2. Control arm: Women will receive GnRH antagonist (Ganirelix 0.25mg) once subcutaneously daily from day 5 of ovarian stimulation till the day of final oocyte maturation

The hMG will be started from day 2 to day 4 in both groups. Oocyte cryopreservation will be applied to collect at least  $7 \pm 1$  oocytes (including frozen and fresh oocytes). In the last ovarian stimulation cycle, the fresh oocytes and all thawed oocytes will be fertilized by ICSI. Freeze all strategy will be applied in both arms, and a single frozen embryo transfer will be performed in the next menstrual cycle.

**Study Duration:**

[figure not shown]
Study Start Date (First patient in): **June, 2023**

Estimated Primary Completion Date (Last patient in): **May, 2027**

Estimated Study Completion Date: **Dec, 2027**

**Participant Duration:**

**2.3. Schema**

#### 2.4. Schedule of activities (SOA)

Stage	Procedure	Before Ovarian stimulation (OS)	OS cycle (repeated in 2 - 3 OS cycles)						Embryo culture	Endometrium preparation	Embryo transfer day	Pregnancy testing	Pregnancy follow-up	
			1st Day of OS	5th Day of OS	8th Day of OS	Trigger day	12h after the trigger shot	OPU day					7th week of pregnancy	12th week of pregnancy
	Visiting	Visit 1	Visit 2	Visit 3	Visit 4	Visit 5	Visit 6	Visit 7	Visit 8	Visit 9	Visit 10	Visit 11	Visit 12	Visit 13
Pre-screening	Information providing		X											
	Demographics		X											
	Medical history		X											
	Pre IVF testing		X											
Screening	Ultrasound			X										
	AMH			X										
	Pre-anesthesia testing and examination			X										
	Informed consent			X										
Enrollment	Randomization			X										
Ovarian stimulation	FSH			X										
	LH			X	X	X	X	X						
	E2			X	X	X	X	X						
	P4			X	X	X	X	X						
	Ultrasound for OS			X	X	X	X							
	OPU								X					
	Oocyte cryopreservation								X					

Stage	Procedure	Before Ovarian stimulation (OS)	OS cycle (repeated in 2 - 3 OS cycles)						Embryo culture	Endometrium preparation	Embryo transfer day	Pregnancy testing	Pregnancy follow-up		
			1st Day of OS	5th Day of OS	8th Day of OS	Trigger day	12h after the trigger shot	OPU day					7th week of pregnancy	12th week of pregnancy	
			Visit 1	Visit 2	Visit 3	Visit 4	Visit 5	Visit 6	Visit 7	Visit 8	Visit 9	Visit 10	Visit 11	Visit 12	Visit 13
Embryo culture	Oocyte thawing (in the last OS cycle)								X						
	ICSI (in the last OS cycle)								X						
	Embryo assessment									X					
	Embryo cryopreservation									X					
Embryo transfer	Ultrasound for ET										X				
	Embryo thawing											X			
	Embryo transfer											X			
Follow-up	bhCG testing												X		
	Ultrasound for Pregnancy Monitoring													X	X
QOL	WHO-BRIEF	X				X									
Report	Adverse event review and evaluation	X	X	X	X	X	X	X	X	X	X	X	X	X	X
	Complete the case report form	X	X	X	X	X	X	X	X	X	X	X	X	X	X

### 3. INTRODUCTION AND RATIONALE

Even when assisted reproductive techniques are offered, ovarian stimulation still is a significant challenge in reproductive medicine. Diminished ovarian reserve (DOR) is often associated with poor ovarian stimulation response, a high cancellation rate, and a significant decline in pregnancy rate during in vitro fertilization (IVF) cycle. Among infertile women, diminished ovarian reserve (DOR) incidence ranges from 6% to 64% at different ages. Based on data of 181,536 fresh, autologous ART cycles reported to SART by US clinics in 2004 and 2011 (1), the prevalence of LOR patients increased from 19 to 26% from 2004 to 2011, and it relates to poor IVF outcomes and low pregnancy rate for these patients (2,3). Unfortunately, the prevalence of DOR has also increased by 42% among patients younger than 40 years old (1). DOR is associated with a decrease in oocyte number and quality and contributes to a decrease in the clinical pregnancy rate and live birth rate and an increase in the miscarriage rate (4). Various studies showed the live birth rate per cycle of 11.1%, 11.4%, and 6.7%, according to ART-register data in the United Kingdom, Canada, and Egypt (5–7). Chang et al. found that young patients with DOR had significantly decreased rates of biochemical pregnancy, clinical pregnancy, and embryo implantation but increased rates of miscarriage compared to young patients without DOR (8).

Several cohort and meta-analysis studies showed that the number of oocytes retrieved for in vitro fertilization (IVF) positively predicts ART treatment (9–11). The appropriate number of oocytes was reported to be between 6 and 15 for optimizing the live birth rate (9,12). If fewer oocytes are retrieved, the live birth delivery rate decreases (9,13). Unfortunately, one of the barriers in patients with DOR is the significantly reduced number of oocytes resulting in fewer oocytes collected and embryos formed. S.J. Morin et al. (2018) reported that the number of oocytes collected in the DOR group (6 oocytes [2-10]) decreased significantly compared to the non-DOR group (14 oocytes [8-19]) ( $P < 0.001$ ). The number of usable blastocysts was also significantly lower in the DOR group than in the non-DOR group (2 embryos [0-3] vs. 4 embryos [1-8]), while the cycles with no usable blastocyst increased significantly (17.0% vs. 5.3%;  $P < 0.001$ ) (14).

Many ovarian stimulation strategies have been proposed to improve oocyte or embryo quantity to increase the chances of embryo transfer and pregnancy outcomes (15,16). Cobo et al. (2012) reported an oocyte storage strategy in LOR patients showing the cumulative live-birth rate was higher in the accumulation group 36.4% (95% CI, 30.3 – 42%) than in the fresh group 23.7% (19.9 – 27.4%,  $P < 0.05$ ) with significant lower embryo-transfer cancellation rate (9.1% of accumulation group vs. 34% of the fresh group) (17). The accumulation of oocytes from several ovarian stimulation cycles is currently possible with the aid of novel vitrification technologies. Therefore, the strategy could potentially increase the number of embryos with comparable success rates and reasonable costs (17–19).

The Progesterone priming ovarian stimulation (PPOS) protocol could be a potential treatment in an oocyte accumulation setting to reduce the financial burden and stress. Progesterone with high concentrations has long been shown to block the LH surge. Its inhibiting role on follicular growth has been the foundation of progestin-only contraceptives, which, after prolonged use, suppress follicular growth and thus block ovulation (20,21). The generation of the LH surge is suggested by two periods: one oestradiol-dependent (early follicular phase) and one oestradiol-independent (late follicular phase) which the signal is transmitted to the GnRH neurosecretory system following the release of the LH surge. If the pituitary gland is exposed to Progesterone for an extended period, Progesterone downregulates its receptors in the pituitary gland (22), inhibiting the pituitary release of LH. Progesterone is essential in inhibiting the estrogen-dependent LH surge pathway (23). Progesterone also involves

slow-down pulsatility of luteinizing hormone in the pituitary gland and hypothalamus (24). Based on the mechanism, the effect was gradually applied to ovarian stimulation. Various studies show that Progestin-primed ovarian stimulation (PPOS) effectively blocks the LH surge in IVF (25–27). Compared with the GnRH antagonist protocol, Chen et al. (2020) showed that the incidence of premature LH surge in the PPOS group was lower than that in the antagonist group (0 vs. 5.88%,  $P < 0.05$ ) (20). PPOS favors segment ART cycles such as FET, oocyte donor, fertility preservation, and oocyte accumulation set. In DOR patients, ovarian could be stimulated in multiple processes to obtain more oocytes for the increasing number of embryos (17). However, numerous stimulation cycles can stress LOR patients as they undergo several procedures, injections, and financial burdens. Instead, the PPOS might be more user-friendly and cheaper than the GnRH antagonist regimen regarding LH suppression during ovarian stimulation (27,28).

Many PPOS protocols have been proposed in which the three most agents include Dydrogesterone (DYG), Microzined Progesterone (MIP), and Medroxyprogesterone acetate (MPA) (20). There were no important differences between the three PPOS protocols in terms of ovarian stimulation response as well as pregnancy outcomes(20,21,29). MIP seems to be of unusual choice because of its vaginal administration. DYG 20 – 30 mg/day has shown to be effective in preventing early LH surge (30,31), although MPA 10 mg/day exerts a more substantial suppression on endogenous LH than DYG (31). However, excessive inhibition of LH levels in the poor response group relates to poor outcomes, and LH supplementation even is indicated in women (32,33). Notably, the extensive worldwide use of DYG for the treatment of threatened and recurrent miscarriage, as well as for the luteal phase support in infertile patients, also suggests its long-term safety (21). Ovarian Stimulation (DPOS) may be an effective and safe protocol in the DOR population.

Nevertheless, data related to the PPOS protocol has not been well documented, including DPOS. More and more centers in China are using the protocol because it is simpler and cheaper (26,34–36). Initial evidence suggests that oocyte quantity and quality are comparable with other ovarian stimulation regimens (20,21,27). Based on retrospective studies, the rate of euploid embryos and the live birth rate were similar in the PPOS group compared with the control group (37,38). However, there has not been an RCT with a large sample size and well-designed to provide more robust evidence. A randomized trial to compare the effectiveness of DPOS and GnRH antagonist protocol in IVF is urgently needed.

#### 4. OBJECTIVES

##### 4.1. Primary objectives:

- To compare the ongoing pregnancy rate per patient in low ovarian reserve patients after accumulation oocyte cycles with either dydrogesterone primed ovarian stimulation (DPOS) or fixed gonadotropin-releasing hormone antagonist (GnRHanta) protocol

##### 4.2. Secondary objectives:

- To compare the characteristics of ovarian stimulation between DPOS and GnRHanta protocol, including LH, Estradiol, and Progesterone profile (Day 1, day 5, and day 8 of ovarian stimulation, final oocyte maturation day, and 12 hours after the final oocyte maturation injection), premature LH rate, the duration of ovarian stimulation and the total dose of FSH, the number of ovarian stimulation cycles.

- To compare the outcomes of the ovarian stimulation between DPOS and GnRH protocol, including number of cumulus-oocyte complexes, number of MII oocytes, oocyte survival rate, fertilization rate, embryo-cleavage rate, blastocyst rate, top-quality blastocyst rate, blastocyst survival rate, implantation rate, positive pregnancy rate, clinical pregnancy rate, early miscarriage rate, multiple pregnancy rate, ectopic pregnancy rate.
- To compare the drop-out rate of DPOS and GnRH protocol in accumulation oocyte cycles of patients with low ovarian reserve
- To assess the safety of DPOS and GnRH protocol in accumulation oocyte cycles of patients with low ovarian reserve.
- To compare the quality of life during ART treatment based on WHO-BRIEF questionnaire

## 5. STUDY DESIGN

This open-label, randomized, controlled, multi-center clinical trial compares the efficacy and safety of the oral Dydrogesterone primed ovarian stimulation versus fixed gonadotropin-releasing hormone antagonist protocol for accumulating oocytes in patients with low ovarian reserve.

- Study Type: Interventional (Clinical Trial)
- Estimated Enrollment: 730 participants (365 per arm)
- Allocation: Randomized
- Intervention Model: Parallel Assignment
- Masking: Open-label
- Primary Purpose: Treatment
- Official Title: Dydrogesterone primed ovarian stimulation versus fixed gonadotropin-releasing hormone antagonist protocol for accumulation of oocyte in patients with low ovarian reserve: A randomized controlled trial

The Study will be conducted according to the following scheme:

### Pre-screening

- **Visit 1** (Day – 180 to 1): The patients who have IVF indication will undergo a physical examination - including vitals sign, a gynecological exam; a review of their medical history and contaminant medication, a transvaginal ultrasound and baseline routine tests (blood tests – including AMH, cervical cancer screening – Pap's smear and HPV, breast ultrasound...). Potentially eligible couples will be given the information sheet about the Study during their first consultation

### Screening and Enrollment

- **Visit 2** (Day 1: the first day of OS cycle - Ovarian stimulation (OS) starts on the 2nd – 4th of mense):
  - The patients undergo a transvaginal ultrasound to access Antral Follicle Count, ovaries and uterus.
  - Laboratory tests (blood tests, urine test and ECG) will be taken for pre-anesthesia examination; in addition, the hormone values include FSH (follicle-stimulating hormone) – only for the first OS cycle, E2 (Estradiol), LH (luteinizing hormone), P4 (Progesterone) and AMH if the result is not

available within 6 months. A pre-anesthesia examination will ensure the patient is eligible for the oocyte retrieval procedure.

- Screening for eligibility will be performed by treating physicians.
- Eligible participants will be invited to a full discussion with investigators about the Study and given the informed consent form. Patients will be given a period (3-4 hours) during anesthesia testing to understand the information and decide whether they agree to participate in the Study. The investigators will obtain written informed consent from all couples before enrolment. To maximize retention in the trial, a consultation will be available to couples to ensure they understand the procedures well and to address any questions or complaints that arise during the Study.

**Treatment period:** The patient will be treated with an oocyte accumulation strategy, and estimated ovarian stimulation cycles range from two to four cycles to collect at least  $7 \pm 1$  oocytes.

*For the first ovarian stimulation cycle:*

- **Visit 2** (Day 1: the first day of OS cycle - Ovarian stimulation (OS) starts on the 2nd – 4th of mense): After informed consent is obtained, the patient will be indicated randomly with one of the following regimens:

**Group I:** oral DYG (Duphaston) 10mg t.i.d from the first day of OS to the day of final oocyte maturation

**Group II:** GnRH antagonist (Ganirelix 0.25 mg) will be initiated on the fifth day of OS to the day of final oocyte maturation

- **Visit 3** (1st cycle - Day 5 of OS): Transvaginal ultrasound and blood sampling (for hormone check-up) will be performed.
- **Visit 4** (1st cycle - Day 8 of OS): Transvaginal ultrasound and blood sampling (for hormone check-up) will be performed.
- **Visit 5** (1st cycle - Day  $10 \pm 2$  of OS): Transvaginal ultrasound and blood sampling (for hormone check-up) will be performed. A final oocyte maturation injection will be performed.
- **Visit 6** (1st cycle - Day  $11 \pm 2$  of OS): blood sampling (for hormone check-up) will be performed after 12 hours of final oocyte maturation injection.
- **Visit 7** (1st cycle - Day  $12 \pm 2$  of OS): Oocyte retrieval and oocyte cryopreservation will be performed. AE/SAE will be recorded routinely.

*For the following ovarian stimulation cycle (s):* the patient will be stimulated with the previous OS protocol. The visits of the patient will be repeated as the first OS cycle.

*For the last ovarian stimulation cycle:* Based on the aim to collect at least  $7 \pm 1$  oocytes, the clinician will determine the last ovarian stimulation cycle on the day of final oocyte maturation. It is defined as a cycle in that the total number of frozen and expected fresh oocytes are at least  $7 \pm 1$  oocytes. The patient will be stimulated with the

previous OS protocol. The visits of the patient will be repeated as the first OS cycle. However, the frozen oocytes of the previous OS cycle will be thawed. All fresh and thawed oocytes will be fertilized by ICSI at **Visit 7**.

- **Visit 8:** (Day 77 ± 7 – Embryo culture report): The patient will receive a Blastocyst embryo culture report and decide whether embryo cryopreservation or not.
- **Visit 9:** (Day 90 ± 7 – Endometrial preparation): Endometrial preparation will start on the 2nd – 4th of mense.
- **Visit 10:** (Day 109 ± 7 – Embryo transfer): Progesterone will be started when endometrial thickness reaches 8 mm or more for 6 - 7 days. Embryo transfer will be performed under ultrasound.
- **Visit 11:** (Day 121 ± 7): On day 11, after embryo transfer, subjects will have a routine pregnancy test (serum β-hCG) to confirm the subject's biochemical pregnancy
- **Visit 12:** (Day 163 ± 7 – Clinical pregnancy confirmation): A transvaginal ultrasound examination will be performed to determine the pregnancy defined as the presence of at least one gestational sac at gestation week 7 ± 1 .
- **Visit 13** (Day 198 ± 7 - End of treatment): A transvaginal ultrasound examination will be performed to determine the Ongoing pregnancy, defined as fetal heartbeats at gestation week 12 ± 1 .

## 6. STUDY POPULATION

Patients come for examination and treatment at ART Unit – Tam Anh TP. Ho Chi Minh General hospital (IVFTA HCM) and Tam Anh General hospital (IVFTA HN)

### 6.1. Inclusion criteria

- Woman age ≤ between 18 and 37 years
- AFC ≤ 5 and/or AMH ≤ 1.2 ng/ml
- Agree to perform freeze-all strategy and single frozen blastocyst embryo transfer

### 6.2. Exclusion criteria

- Oocyte recipient
- Indication of preimplantation genetic testing
- Known allergic reactions to medications in the Study (progesterone products, GnRH antagonist....)
- Basal FSH above 15mIU/mL.
- Have contraindications of ART treatment (e.g. critical or acute diseases)
- Retrieved sperm
- Repeated Implantation failure ( ≥ 3 failed embryo transfers with good-quality embryos)
- Inability to comply with the study procedures.
- Patients with a history of thyroid cancer who are on hormone replacement therapy or those diagnosed with thyroid diseases at the time of eligibility assessment

## 7. STUDY INTERVENTION

### 7.1. Pre-screening

At **Visit 1**, the couples with IVF indication will undergo a physical examination - including vitals signs, a gynecological exam; a review of their medical history and contaminant medication, a transvaginal ultrasound, and baseline routine tests. The blood tests include total blood count, blood group, AMH (within 6 months), TSH, FT4, Anti-TPO, HIV, HCV, HBsAg, Syphilis, Tuberculosis, Rubella, Chlamydia PCR, Pap's smear and HPV, breast ultrasound. Potentially eligible couples will be given the information sheet about the Study during their first consultation (**Visit 1**).

## 7.2. Screening and Enrollment

The patients will be checked for inclusion criteria on the second - fourth menstrual day (Visit 2). Laboratory tests (blood tests, urine test and ECG) will be taken for pre-anesthesia examination; in addition, the hormone values include FSH (follicle-stimulating hormone) – only for the first OS cycle, E2 (Estradiol), LH (Luteinizing hormone), P4 (Progesterone) and AMH if the result is not available within 6 months. A pre-anesthesia examination will be performed to ensure that the patient is eligible for the oocyte retrieval procedure.

On the day (Visit 2), screening for eligibility will be performed by treating physicians. If the patients are eligible, we will invite them to a full discussion about the Study and give the informed consent form. We will inform verbal and written consent and explain the relevant information such as study context, objectives, and data collection procedure. Patients will be given a period (3-4 hours) during anesthesia testing to understand the information and decide whether they agree to participate in the Study. The investigators will obtain written informed consent from all couples before enrolment. To maximize retention in the trial, a consultation will be available to couples to ensure they understand the procedures well and to address any questions or complaints that arise during the Study.

When there is an eligible participant to be enrolled in the Study, clinicians from the specific site will enter the study data management center to get the allocation of patients according to a computer-generated randomization list in a 1:1 ratio, with a variable block size of 2, 4, 6 or 8. After randomization, if a participant wishes to change her assigned protocol in the first cycle, she will be considered a crossover but analysed in the group she was assigned (intention-to-treat). However, if she wishes to change the assigned protocol from the second ovarian stimulation cycle or transfer more than one embryo after randomization, it will be considered a protocol violation and excluded from the analysis. Due to the type of interventions, this Study will be label-opened to clinicians who perform ovarian stimulation, oocyte retrieval, and embryo transfer.

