stimulation cycle, the fresh oocytes and all thawed oocytes will be fertilized by ICSI. The freeze-all strategy will be applied in both arms, and single blastocyst frozen embryo transfer will be performed in the next menstrual cycle.

The ongoing pregnancy rate of patients in IVFTA HCM was 45.0% in the Antagonist IVF stimulation group. To show or refute that hypothesis: no significant difference in ongoing pregnancy rates when using DPOS protocol (40 - 42%), we need 657 patients to produce a two-sided 95% confidence interval for the difference in population proportions with a width that is equal to 5% (margin = 5.0%, alpha = 5.0% and power = 80%). Considering a 10% loss to follow-up and protocol violation, we plan to recruit 730 participants (365 per arm). The primary endpoint is the ongoing pregnancy rate after the first completed transfer. Secondary endpoints are ovarian stimulation, embryo culture characteristics, drop-out rate, and DPOS and GnRH antagonist protocol safety.

All analyses will be performed on an intention-to-treat basis using the R statistical package

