Miscarriage	Complete loss of clinical pregnancy at 12 weeks of gestation
Multiple pregnancy rate	Multiple pregnancy rate is explained as two or more gestational sacs or positive heartbeats by transvaginal sonography 5 weeks after embryo placement
Ectopic pregnancy rate	Ectopic nidation of pregnancy confirmed by sonography or laparoscopy at 12 weeks of gestation
OHSS	Ovarian hyperstimulation is diagnosed according to RCOG guideline 2016
Known Adverse events regarding medications	
Adverse events regarding medications according to local information products - including:
 
 
• Duphaston: Abdominal pain, bloating, severe headache, dizziness, depression, hot flushes, abnormal vaginal discharge, joint pain, urinary problems or nausea, fatigue or extreme tiredness, somnolence or sleepiness, vaginal hemorrhage, pruritus (severe itching of the skin).
 
• Orgalutran: redness, pain or swelling at injection site, headache, nausea, tiredness.
 

	
 
• Diphereline: nausea, tiredness, mood changes, depression, redness, swelling, pain and /or bruising at the injection site, swelling of the hands and feet (edema) muscle and bone pain, pain in arms and legs, dizziness, headache, impotence, loss of libido.
 
• Ovitrelle: injection site, headache, vomiting, nausea (feeling sick), abdominal (belly) pain, abdominal distension (feeling of bloating)
 
• Valiera: Headache, nausea, breast pain, abdominal cramp, bloating, vaginal spotting.
 
• Cyclogest: Abdominal distension (swelling in the abdomen), abdominal pain, constipation, sleepiness, tiredness, hot flush, breast pain.
 
• IVF-M: Headache, injection site pain, injection site allergic reaction, abdominal pain, abdominal cramps or nausea.
 

Drop-out	Drop-out is defined as any patient discontinuing the Study or the investigator withdrawing them from the Study for any reason.
Quality of life score	Quality of life is assessed by Vietnamese WHO-BRIEF questionnaire

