### **12.3. Statistical analyses**

Statistical analysis will be conducted according to the ITT principle, in which all randomized women will be conducted for the comparison of primary outcomes between treatment groups. The per-protocol analysis may be conducted, but these results would be considered reference only. All tests will be two-tailed, and differences with p-value < 0.05 will be considered statistically significant. The statistical software used was R, version 4.0.5 (R Foundation for Statistical Computing). We will develop a detailed statistical analysis plan that will be completed before data-lock.

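### Read as written, the intention-to-treat wording for all analyses also counts crossovers' adverse events in the assigned arm, which shrinks arm-level safety differences by an amount the protocol gives no means to judge

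*Protocol*

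**What the plan says.** The closing line of Protocol 2.1 reads "All analyses will be performed on an intention-to-treat basis using the R statistical package". Section 7.2 sets two rules for women who change regimen:

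- A change in the first cycle: "she will be considered a crossover but analysed in the group she was assigned (intention-to-treat").
- A change from the second cycle on: "it will be considered a protocol violation and excluded from the analysis".

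Safety is among the things to be analysed. Section 4.2 has the objective "To assess the safety of DPOS and GnRH protocol in accumulation oocyte cycles of patients with low ovarian reserve". The endpoint list in the synopsis (2.2) ends with "drop-out rate, OHSS rate, and adverse events". Table 2 in section 8 describes the known events as "Adverse events regarding medications according to local information products" and lists them product by product, for example "Orgalutran: redness, pain or swelling at injection site, headache, nausea, tiredness".

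Section 12.3 is narrower than 2.1. Under the intention-to-treat principle, it says, "all randomized women will be conducted for the comparison of primary outcomes between treatment groups". It also allows an optional per-protocol analysis, for reference only. Section 12.3.3 gives methods for secondary outcomes but names no analysis set. No safety set and no analysis by treatment received appears in the protocol.

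**The concern.** Counting women as randomised is right for ongoing pregnancy. For harms, the usual question is also what happens to women who take a regimen, and a count by assignment alone does not answer it when some women take the other one.

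The protocol expects switching, since it writes a rule for it, and the trial is open-label with an oral regimen against a daily injection. Sections 5 and 7.3.2 repeat the previous regimen in later cycles. A first-cycle crossover may therefore stay on the other regimen for all of her stimulation cycles, with her events counted in the assigned arm throughout. Women who switch later drop out of the analysis. Under these two rules, no switcher's events are ever counted under the regimen she took, and a real difference between the regimens would look smaller than it is.

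**Working it through.** The protocol states no figure on this point, so there is none to reproduce. The check has two parts.

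**1. Does the text reach safety?** Section 2.1 covers all analyses. Adverse events and OHSS are secondary endpoints (2.2) under a stated objective (4.2). Section 7.2 fixes the group for first-cycle crossovers without limiting this to efficacy. Section 12.3 mentions only the primary outcome. So 2.1 and 7.2 together include safety, while 12.3 neither includes nor excludes it.

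**2. How large is the shrinkage?** Let pA and pB be the true event rates on the two regimens, and c the share taking the other regimen. Assume a complete switch before any exposure, and an event rate that depends only on the regimen taken.

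- Arm A as assigned: (1-c)·pA + c·pB
- Arm B as assigned: (1-c)·pB + c·pA
- Difference with switching in both arms: (1-2c)·(pB - pA)
- Difference with switching in one arm only: (1-c)·(pB - pA)

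Example with assumed rates of 5% and 10% and c = 10% each way: 0.9×0.05 + 0.1×0.10 = 0.055, and 0.9×0.10 + 0.1×0.05 = 0.095. The difference is 4.0 points instead of 5.0, a ratio of 0.80.

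The table shows the range. The switch rates and event rates are assumptions; 365 per arm is from 12.1. Power is for a two-sided 5% test of two proportions with switching in both arms.

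| c | Kept, both arms switch | Kept, one arm switches | Power, 5% vs 10% | Power, 10% vs 20% |
|---|---|---|---|---|
| 0% | 100% | 100% | 73% | 97% |
| 1% | 98% | 99% | 71% | 96% |
| 2% | 96% | 98% | 69% | 95% |
| 5% | 90% | 95% | 64% | 93% |
| 10% | 80% | 90% | 54% | 86% |
| 20% | 60% | 80% | 34% | 62% |

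The loss is thus 1-4% of the difference at 1-2% switching and 10-20% at 10% switching. A woman who switches partway through a cycle has been exposed to both regimens, so the formula overstates her contribution. If women switch because of an event, the assumption of equal risk given the regimen also fails, and the factor is then only a guide.

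**The case against.** The strongest reply is that the protocol does not say in so many words that adverse events are analysed by assigned arm. That follows only from one general sentence in the summary together with 7.2. The operative section, 12.3, attaches intention-to-treat to the primary outcome and promises a detailed analysis plan before data-lock, and a safety set is ordinary content for such a plan. This stands in part. A SAP could add the set, but it would then depart from what 2.1 says of all analyses, so the protocol wording needs correcting in any case.

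A reader might go further and infer that events are charged to a drug the woman never took. The documents do not support that. Each event is assessed for its causal relation to the drug (11.2.2), and medication-related events are asked about at every retrieval (11.2.1). Only the count per arm is affected.

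Nor are injection-site reactions a clean example. Table 2 lists them for the gonadotrophin and the trigger drugs as well, and 7.3.1 gives these to both arms. Dydrogesterone is given to all women at frozen transfer (7.3.5), so its events at that stage do not separate the arms under either counting rule.

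It is also tempting to say that one misplaced serious event could reverse the picture, or that shrinkage favours a claim of equal safety. SAEs are reported individually (11.3.2) and adverse events are adjudicated by the DSMB (12.3.5). The objective is to assess safety, and no equivalence or non-inferiority claim for safety is stated.

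Finally, a comparison by regimen received gives up randomisation. That is true, and it is why such a table should stand beside the as-assigned one and not replace it.

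**Conclusion.** The point holds in a limited form. As worded, 2.1 and 7.2 place crossovers' adverse events in the assigned arm, and no table by regimen received is foreseen. Any true between-arm difference in regimen-related events during the stimulation cycles then shrinks by the factor (1-2c), or (1-c) if only one arm switches.

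The size cannot be fixed from the documents, which give neither a crossover rate nor event rates. It is negligible if almost nobody switches and material from about 10%. The conclusion rests on reading the general sentence in 2.1 literally, on complete switches, and on switchers having the same risk as others on the same regimen. It does not touch the primary efficacy analysis. This is a low-cost improvement to the stated rule; it does not show that the safety results will mislead.

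**What to change.** - In 2.1, limit the intention-to-treat statement to efficacy, in line with 12.3.
- In 12.3.3, add a comparison of adverse events, SAEs and OHSS by the regimen actually received in each stimulation cycle, shown beside the as-assigned table.
- State that events before a mid-cycle switch are attributed to the regimen taken up to then.
- Keep women who switch from the second cycle on in the safety tables instead of excluding them.
- Report the number of crossovers per arm, so that the reader can judge how far the two tables could differ.

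The cost is a few sentences and one further table. Adverse events are already recorded at every visit, and the action taken with study drug is recorded for each event (11.2.2). The one item to confirm is that the CRF holds the date of any switch. The drawback is that the table by regimen received is not a randomised comparison, which is why the as-assigned table stays.
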